12 CONSENT PROCESS

The investigator will ensure that this study is conducted in full conformity with Regulations for the Protection of Human Subjects of Research codified in 45 CFR Part 46, 21 CFR Part 50, 21 CFR Part 56, and/or the ICH E6.

The protocol, informed consent form(s), recruitment materials, and all participant materials will be submitted to the IRB for review and approval. Approval of both the protocol and the consent form must be obtained before any participant is enrolled. Any amendment to the protocol will require review and approval by the IRB before the changes are implemented to the study. All changes to the consent form will be IRB approved; a determination will be made regarding whether previously consented participants need to be re-consented.

Consent forms describing in detail the study agent, study procedures, and risks are given to the participant and written documentation of informed consent is required prior to starting intervention/administering study product. The following consent materials are submitted with this protocol:

Informed consent is a process that is initiated prior to the individual's agreeing to participate in the study and continues throughout the individual's study participation. Extensive discussion of risks and possible benefits of participation will be provided to the participants and their families. Consent forms will be IRB-approved and the participant will be asked to read and review the document. The investigator will explain the research study to the participant and answer any questions that may arise. All participants will receive a verbal explanation in terms suited to their comprehension of the purposes, procedures, and potential risks of the study and of their rights as research participants. Participants will have the opportunity to carefully review the written consent form and ask questions prior to signing.

The participants should have the opportunity to discuss the study with their surrogates or think about it prior to agreeing to participate. The participant will sign the informed consent document prior to any procedures being done specifically for the study. The participants may withdraw consent at any time throughout the course of the trial. A copy of the informed consent document will be given to the participants for their records. The rights and welfare of the participants will be protected by emphasizing to them that the quality of their medical care will not be adversely affected if they decline to participate in this study.

13 PLANS FOR PUBLICATION

Year 5 of the study will entail data processing and interpretation and writing of a paper for publication.

15 APPENDIX

Figure 1

Repeat the above for 50% Cho (275 mg/d) and 100% Cho (550 mg/d). Arms performed in random order with minimum 2 week washout in between.

Figure 1 outlines what each 2 week intervention period is comprised of. This will be completed 3 times per subject.

[figure not shown]
Figure 2

Figure 3

Pathway	Metabolite	Platform ²	Fatty liver		Muscle dysfunction		No dysfunction	
			D/B ¹	R/D ¹	D/B ¹	R/D ¹	D/B ¹	R/D ¹
Choline metabolism	Choline	T-LC/MS	0.67	1.50	0.66	1.25	0.71	NA
	Sarcosine	T-GC/MS	0.47	2.00	0.60	1.08	0.56	NA
	Dimethylglycine	T-GC/MS	0.51	1.81	0.55	1.41	0.59	NA
	Betaine	T-LC/MS	0.45	1.66	0.53	1.07	0.47	NA
	Methionine	T-GC/MS	0.86	1.10	0.93	1.01	0.96	NA
	Phosphatidylcholine (total)	T-LC/MS	0.89	1.08	0.90	1.06	0.97	NA
Carnitine metabolism	Homocysteine	T-GC/MS	1.16	0.97	1.19	0.99	1.27	NA
	Carnitine	N-LC/MS+	1.41	0.84	1.23	1.02	1.42	NA
	Butyrylcarnitine	N-LC/MS+	1.23	0.89	1.03	1.13	1.30	NA
	Isobutyrylcarnitine	N-LC/MS+	1.09	1.12	0.88	1.44	1.41	NA
	Isovalerylcarnitine	N-LC/MS+	0.75	1.36	1.01	0.88	0.87	NA
Renal transporter	Propionylcarnitine	N-LC/MS+	1.02	0.99	1.38	1.38	1.78	NA
	Hippurate	N-LC/MS+	0.53	1.88	0.93	0.72	0.75	NA
	3-indolepropionate	N-LC/MS+	0.74	1.03	1.08	0.62	0.50	NA
	CMPF	N-LC/MS-	0.46	0.86	0.57	0.74	0.32	NA
Keto acid metabolism	Creatinine	N-LC/MS+	1.00	0.95	1.00	1.00	1.12	NA
	Myo-inositol	N-GC/MS	0.70	1.22	0.85	1.13	0.76	NA
	Pyridoxate	N-LC/MS-	0.71	1.18	0.93	1.09	0.82	NA
Cell death	Erythronate	N-GC/MS	1.11	0.90	1.21	0.97	1.24	NA
	Urate	T-Clin Lab	1.19	0.90	1.39	0.92	1.22	NA
Amino acid metabolism	Pseudouridine	N-GC/MS	1.17	0.92	1.28	0.98	1.20	NA
	Glutamine	N-LC/MS+	1.07	0.87	1.06	0.98	1.12	NA
	Pyroglutamate	N-LC/MS-	1.29	1.06	1.08	1.03	1.36	NA
	Valine	N-LC/MS+	1.03	1.01	0.97	1.06	1.13	NA
	Glutamylvaline	N-LC/MS+	1.19	0.91	1.37	1.20	1.47	NA
	Glycine	N-GC/MS	1.12	0.89	1.09	0.98	1.09	NA
	Leucine	N-LC/MS+	1.01	1.03	0.87	1.45	1.25	NA
	Trans-4-hydroxyproline	N-GC/MS	1.01	1.35	0.70	0.89	1.18	NA
Diet	Stachydrine	N-LC/MS+	0.06	5.39	0.10	0.86	0.03	NA
Fatty liver	Ratio of liver fat to spleen fat	MRS	1.55	0.72	1.18	0.82	1.12	NA
	X - 02249	N-LC/MS-	0.63	1.60	0.57	0.98	0.67	NA
Unknown	X - 09789	N-LC/MS-	0.30	2.98	0.23	1.71	0.32	NA
	X - 11315	N-LC/MS+	0.82	0.95	1.03	0.92	0.84	NA
	X - 11787	N-LC/MS+	1.46	0.84	1.39	1.19	1.74	NA
	X - 11849	N-LC/MS-	1.50	1.28	5.76	1.37	6.00	NA
	X - 11876	N-LC/MS-	1.88	0.69	1.45	1.25	1.74	NA

Fig. 3. Metabolites that significantly changed in intensity after Cho depletion. Human subjects were fed diets with Cho, then deprived of Cho, and then repleted with Cho. Some of the subjects developed organ dysfunction (liver or muscle) when deprived of Cho, others did not (No dysfunction). Plasma samples were collected at the end of each diet period and analyzed by targeted and nontargeted biochemical assays. Fold change between depletion and baseline (D/B) and between repletion and depletion (R/D) are shown, with significant changes (FDR adjusted $P < 0.05$) underscored. Fold change that indicates an increase by Cho depletion or repletion is shaded red; change that indicates a decrease is shaded green. NA, not performed. From (10).

[figure not shown]
Figure 4

Figure 4: Cho status score correlates with Cho pool size. We propose that as Cho pools become depleted, a decrease in concentrations of plasma Cho and PtdCho occurs early. As Cho pools decrease further, other markers of altered 1-carbon metabolism change and cellular dysfunction due to lack of Cho starts, and various metabolite, enzyme and functional markers reflecting this dysfunction begin to rise. Though there may be many causes of dysfunction for a particular organ, the pattern of organ dysfunction combined with specific Cho metabolites provides a distinct signature for Cho depletion. A Cho status score based on this signature should correlate well with Cho pool size as measured by isotopic dilution.

[figure not shown]

Figure 5: (modified from (89)). Distribution of deuterium from Cho chloride-(trimethyl-d9) in metabolites that appear in plasma.

Figure 6: Abnormal lab results – Action Protocol

CK level Normal range Males – 24-204 U/L Females – 24-173 U/L	Real change is considered $\geq 5X$ upper range of normal – level required to be considered a real change for statistical outcome calculations	Monitoring level - $\geq 50X$ upper range of normal. This level indicates that additional monitoring should be performed to assess clinical relevance.	Stopping level (STOP) – $\geq 125X$ upper range normal. This level requires stopping subject's continued participation in the study.
	No need for IRB – AE reporting	Report to IRB with the description of plan of action.	Report to IRB as AE with the description of plan of action.
	
Plan of action:
 
1. Repeat labs to include (CK/CMP) in 1 week – if still high and increasing then repeat in 24hrs (Discussed with MD plan of action)
 
-if still high but decreasing then repeat in 2 weeks until normalization
	
Plan of action:
 
1. Repeat labs (CK/CMP)
 
2. Add myoglobin urine test
 
4. Assess eGFR (from CMP), determine if eGFR has decreased from baseline values to <60. Send ALL labs STAT.
 
*If Myoglobin is <5mg/L and if eGFR has not declined from baseline values, then consider keeping subject in the study as long as the CK normalizes before next ARM of the study.
 
* Recheck CK in 1 week again until normalization.
 
* If Myoglobin in urine is >5mg/L or if eGFR has declined to <60 –stop subject's continued participation in the study and feed a diet containing 100% choline requirement until value normalizes.
 
5. Refer subject to their own physician for followup.
	
Plan of action:
 
1. STOP subject's participation in the study.
 
2. Repeat labs (CK/CMP)
 
3. Add GGT blood test
 
4. Add myoglobin urine test
 
5. Assess eGFR (from CMP), determine if eGFR has decreased from baseline values to <60. Send ALL labs STAT.
 
6. Subject to be placed on 100% choline diet.
 
7. Follow up labs weekly until normalization.
 
8. Refer subject to their own physician for followup.

AE – adverse event, CK – creatine kinase, CMP – comprehensive metabolic panel, eGFR-estimated glomerular filtration rate, GGT-gamma-glutamyl transferase

Myoglobin in urine – Normal levels are usually 0 to less than 1 mg/L.

Results between 1 and 15 mg/L are associated with vigorous exercise, myocardial infarct, mild muscle injury, and other conditions.

Patients with urine myoglobin greater than 15 mg/L are at risk of acute renal failure.

Tea color urine (visible myoglobinuria) – usually occurs when myoglobin >250 micrograms/ml (normal is < 5nanograms/ml) – which corresponds to a destruction of > 100gm of muscle tissue.

Scalco RS, et al. BMJ Open Sport Exerc Med 2016;2:e000151. Doi:10.1136/bmjsem-2016-000151

Abnormal AST/ALT levels in the ABSENCE of increased CK – protocol for action

AST/ALT results AST Normal range 0-40 IU/L ALT Normal range Males – 0-44 IU/L Females – 0-32 IU/L	Real change is considered $\geq 1.5 \times$ upper range of normal – level required to be considered a real change for statistical outcome calculations	Monitoring level is $\geq 2.5 \times$ upper range of normal. This level indicates that additional monitoring should be performed to assess clinical relevance.	Stopping level (STOP) is $\geq 5 \times$ upper range normal. This level requires stopping subject's continued participation in the study.
	No need for IRB –AE reporting	Report to IRB with the description of plan of action.	Report to IRB as AE with the description of plan of action.
	Plan of action: 1. Repeat labs (CMP only) in 1 week – if still high and increasing then repeat in 24hrs (Discussed with MD plan of action/possible etiology) --if still high but decreasing then repeat in 2 weeks until normalization	Plan of action: 1. Repeat labs (CMP) 2. Add GGT blood test (if $\geq 2.5 \times$ upper range of normal possible indication of alcohol consumption and noncompliance with study) May consider then moving to stop subject from the study. Send ALL labs STAT 3. GGT is $< 2.5 \times$ the upper range of normal then consider keeping the subject in the study as long as the AST/ALT and GTT normalize before next ARM. * Recheck AST/ALT and GTT in 1 week again until normalization.	Plan of action: 1. STOP subject participation in study. 2. Repeat labs (CMP) 3. Add GGT blood test. Send ALL labs STAT. 4. Subject to return to his general normal diet. 5. Follow up labs weekly until normalization. 6. Refer subject to their own physician for followup

ALT-alanine aminotransferase, AST-Aspartate aminotransferase

Version Mar_7_2018

Intervention protocol template_18Dec2018

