Test Article(s) (If Applicable)	The experimental diets, delivering 100%, 50% (to be determined by a pilot study) and 25% of the recommended intake of Cho (in all forms) (550 mg Cho/70 kg body weight/d), are identical except for the bread that we offer (Cho in the bread will be varied to deliver the desired Cho above that delivered by the base 25% Cho diet as described previously (1)). On day 12 of a diet period, subjects will consume 250mg Cho in the form of Cho chloride (trimethyl-d9). We will confirm total Cho content of diets by LC-MS/MS analysis of samples of duplicate food portions as previously described (1).

Study Design	Healthy volunteers (n=50 males, 50 premenopausal females and 50 postmenopausal females; 30 additional subjects for dropout replacement), will be randomly assigned to an order of 2 week intervals of diets where they consume meals that we provide containing 100% of the recommended intake of Cho (550 mg Cho/day), 50% of the recommended intake of Cho (275 mg Cho), and 25% of the recommended intake of Cho (137.5 mg Cho) for 2 weeks each. Each dietary interval is followed by a minimum 2 week washout period. On day 12 of each diet period, subjects will consume a bolus of 250mg of Cho in the form of Cho chloride-(trimethyl-d9). Before this bolus, a plasma sample will be collected to measure baseline enrichment of Cho isotopes. At the end of each diet period, plasma and urine samples will be collected for biomarker assays and isotopic dilution estimation of Cho pool size, and we will perform transient elastography (Fibroscan) of liver to assess liver fat. (see Fig. 1, appendix).

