People need to have a source of Cho: Cho has several important functions. It is (i) a source of methyl-groups needed to make the primary methyl donor, S-adenosylmethionine; (ii) a part of the neurotransmitter acetylCho; and (iii) a component of the major phospholipids in membranes (phosphatidylCho (PtdCho) and sphingomyelin)

(13). The Cho derivative, PtdCho is a main constituent of very low density lipoproteins (VLDL) and is required for VLDL secretion and the export of fat from liver (14). Cho also is important for normal fetal development (15, 16).

Cho is a required nutrient and in 1998, an Adequate Intake (AI) and a Tolerable Upper Limit (UL) for Cho was established (17). In 2016, the US Food and Drug Administration (FDA) set a Recommended Daily Intake (RDI) for Cho based on the AIs as part of the new Nutrition Facts label for packaged foods (published in the Federal Register on May 27, 2016; FDA-2012-N-1210-0875, Federal Register Number:2016-11867). The AI/RDI varies by age and gender, but is 550 mg/d in adult men and 425 mg/d in adult women (more in pregnant and lactating women).

Dietary Cho intake varies over a 3-fold range: There is a wide variation in Cho intake in the diet; in several human cohorts, Cho intake varies by approximately 3-fold – the US National Health and Nutrition Examination Survey (NHANES 2009-2012) data show that only 11% of adult Americans achieve the Adequate Intake level of Cho, with mean intake being 300 mg/day (10%ile being 200 mg/d; 90%ile being 500 mg/d) (2). Similar ranges of intake were reported in the Framingham Offspring Study (18), the Atherosclerosis Risk In Communities study (19, 20) and the Nurse's Health Study (21). Intake of Cho is even lower in low-income countries such as Jamaica and The Gambia (22, 23).

[figure not shown]

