for Cho we have demonstrated that self-report can significantly underestimate actual intake (60). Thus, we need a set of biomarkers with which to assess Cho status in people. The largest stores of Cho are located in the liver, and mass resonance spectroscopy of liver has been used in the past to assess Cho status in humans (3, 25, 51). This method is not practical for use as a biomarker in clinical or public health practice as it is expensive and the availability of the instrumentation is limited. Liver biopsy is risky and not practical, making measurement of hepatic Cho and Cho metabolite concentrations a poor choice for assessing Cho status. Measurement of Cho concentrations in plasma alone is not an adequate marker for Cho status because Cho concentrations drop quickly to 70% of normal when a person is fed a low Cho diet, but do not decrease further with more severe depletion (3, 4) even in people starved for 7 days (61). The concentrations of PtdCho and sphingomyelin also decrease in people fed a low Cho diet (3, 4), but these phospholipids alone are not adequate biomarkers for Cho status because they are carried as part of plasma lipoproteins, and vary in concentration with changes in fat and cholesterol transport by these particles. Thus, such measurements are useful but not sufficient as biomarkers for Cho status.

Perhaps there is a panel of biomarkers that together will more accurately and reliably reflect Cho status. We admitted people (n=169; 60 premenopausal women, 52 postmenopausal women and 57 men) to our CTSA and fed them a diet containing 100% of recommended intake (550 mg/d) for one week, and then fed them a low Cho diet (10% normal Cho) for up to 7 weeks, or until they developed liver or muscle damage, and then fed them a Cho replete diet until such damage was completely resolved (24, 25, 52, 55). In these carefully controlled studies, using n=44 of the subjects, a comparison of metabolomic profiles between the two diet periods identified a number of potentially useful biomarkers of Cho status (10) (**Figs 2 & 3**).

The concentrations of plasma Cho, betaine, sarcosine, dimethylglycine, methionine, and PtdCho were significantly decreased, and homocysteine was significantly increased during Cho depletion in people (10). Cho

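### Figure 6 puts subjects stopped for CK on the 100% choline diet but returns those stopped for AST/ALT to their usual diet, with no reason given; aligning the two is a cheap safety improvement

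*Combined protocol and SAP*

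**What the plan says.** Figure 6 (Section 15, Appendix) sets out what to do when safety laboratory values are abnormal, with one chart for CK and one for AST/ALT. The second chart is limited by its title: "Abnormal AST/ALT levels in the ABSENCE of increased CK".

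The CK chart can stop a subject in two ways, and both name a diet. At the stopping level the step is "Subject to be placed on 100% choline diet". At the monitoring level, if urine myoglobin or eGFR is abnormal, staff are to stop the subject and "feed a diet containing 100% choline requirement until value normalizes".

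The AST/ALT chart can also stop a subject in two ways. At the stopping level, step 4 reads "Subject to return to his general normal diet". It carries no condition on cause, GGT result or diet arm. At the monitoring level, a high GGT may lead to a stop at staff discretion, and no diet is named.

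The withdrawal paragraph in Section 4.6 sends withdrawn or terminated subjects with abnormal results to this same figure and adds weekly panels until values are normal. It names no diet either.

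**The concern.** The protocol treats liver and muscle damage as twin consequences of choline depletion and reports a single dietary remedy for both. Sections 1.3 and 5.3 say that both kinds of damage reversed within two weeks on the 100% diet. Section 1.1 says of the earlier depletion studies that investigators "then fed them a Cho replete diet until such damage was completely resolved". No section reports recovery of the liver on a usual diet, and none explains why a liver stop should be handled differently from a muscle stop.

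What is at stake is the care of a subject with choline-related liver injury who is stopped on the 25% or 50% arm. Step 4 does not prolong the study's depletion, since the low-choline diet ends. It leaves out the repletion that a CK-stopped subject on the same arm would receive. The estimates and the planned analyses are not involved.

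**Working it through.** The plan states no figure to reproduce. The check is a comparison of instructions, followed by simple ratios.

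**1. Stop routes side by side (Figure 6).**

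| Route | Trigger | Diet named |
|---|---|---|
| CK, stopping level | at least 125 × upper normal | 100% choline |
| CK, monitoring level with stop | at least 50 ×, with myoglobin >5 mg/L or eGFR decline to <60 | 100% choline until normal |
| AST/ALT, stopping level | at least 5 ×, CK not raised | usual diet |
| AST/ALT, monitoring level, discretionary stop | at least 2.5 ×, with GGT at least 2.5 × | none |

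The 100% diet is named in 2 of 2 CK routes and 0 of 2 AST/ALT routes. The contrast holds only among stopped subjects: those kept in the study at the monitoring level are not prescribed the 100% diet in either chart.

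**2. Stopping thresholds, from the normal ranges in Figure 6.** AST: 5 × 40 = 200 IU/L. ALT: 5 × 44 = 220 IU/L in men and 5 × 32 = 160 IU/L in women.

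**3. Evidence of reversal.** Sections 1.1, 1.3 and 5.3 each tie recovery to a replete or 100% choline diet. In Sections 1.3 and 5.3 the damage followed more than two weeks on a 10% diet, which is deeper depletion than this trial plans. One title in the reference list mentions reversal with intravenous choline during parenteral nutrition. That too is repletion, but not by diet.

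**4. Possible size of the choline gap.** Section 1.1 gives US survey intake as "mean intake being 300 mg/day (10%ile being 200 mg/d; 90%ile being 500 mg/d". The Synopsis defines the full diet as "100% of the recommended intake of Cho (550 mg Cho/day". Section 1.1 gives the women's Adequate Intake as 425 mg/d. Assuming 70 kg body weight and subjects who eat like the survey population:

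| Usual intake | Share of 550 mg/d | Share of 425 mg/d |
|---|---|---|
| 200 mg/d (10th percentile) | 200/550 = 36.4% | 200/425 = 47.1% |
| 300 mg/d (mean) | 300/550 = 54.5% | 300/425 = 70.6% |
| 500 mg/d (90th percentile) | 500/550 = 90.9% | 500/425 = 117.6% |

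**5. Why these ratios are weak.** Section 1.1 also warns that for choline "self-report can significantly underestimate actual intake". The title of the source cited for that statement (reference 60 in Section 14) says that freely chosen intake in healthy people reaches or exceeds the adequate intake. Only the title is available here, but the trial enrols healthy volunteers. If it applies to them, the shortfall from the recommended intake is nil. The range therefore runs from no gap up to the survey figures above.

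**The case against.** The strongest case for leaving step 4 alone has five parts.

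- **The usual diet has already been tested in each subject.** Section 3.4 admits only people judged healthy on examination and standard laboratory tests, and they were eating their usual diet at the time. This stands. It is not evidence of reversal after injury, but it bears on whether that diet is adequate for that person.
- **The design already relies on the usual diet.** Each washout of at least two weeks prescribes no study diet, so a subject stopped at the end of a period does what other subjects apparently do next. This stands as context. Those other subjects do not have enzymes at five times the upper limit.
- **An isolated AST/ALT rise may have another cause.** Sections 1.3 and 5.3 report no clinically significant damage after two weeks or less on a 10% diet, and the monitoring column raises alcohol as a possibility. Section 9 uses recovery on withdrawal of the diet when grading causality, and a return to the usual diet serves that purpose. This is a fair rationale, but the protocol does not state it, and step 4 applies to every subject whatever the cause. A physician exception meets the point.
- **Follow-up is already in place.** Repeat tests, GGT, weekly panels, IRB reporting and physician referral all apply. This stands and limits the consequence.
- **Section 8 puts all subjects on the 100% diet for the last two weeks.** This does not help. That text describes a non-randomised sequence at odds with the random order in Section 3.1, and it does not address subjects stopped early.

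A reader might go further and infer that a stopped subject would be expected to miss (550 − 300) × 14 = 3,500 mg of choline over two weeks, or that the usual diet would leave the liver injury unresolved. The documents support neither. The 3,500 mg takes the survey mean at face value, against the protocol's own warning about self-report and the title it cites. No passage shows a failure to recover on a usual diet.

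**Conclusion.** This is a cheap safety improvement, not a demonstrated error. Figure 6 prescribes the 100% choline diet in both CK stop routes and in neither AST/ALT stop route. It gives no reason, although the only dietary reversal of liver damage that the protocol reports is on a replete or 100% choline diet.

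The benefit cannot be sized. At the survey mean the usual diet supplies 54.5% of the 550 mg/d diet, or 70.6% of the women's Adequate Intake, and the true shortfall could be nil. These ratios assume 70 kg body weight and survey-like eating. The number of stops is not given and should be very small, since a harsher diet for up to two weeks caused no clinically significant damage. The case for the change rests on consistency with the protocol's own handling of CK stops and on low cost, not on an expected deficit.

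**What to change.** In the AST/ALT chart of Figure 6, stopping column, replace step 4 with wording such as:

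> Feed the 100% choline diet until AST and ALT are normal, unless the stop occurs on the 100% arm, or the study physician judges the cause unrelated to choline or suspects the study meals. In those cases the subject resumes the usual diet and the reason is recorded.

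Apply the same wording to the discretionary GGT-based stop in the monitoring column. A high GGT alone should not settle the physician's judgement there, because the chart calls it only a possible sign of alcohol use and non-compliance.

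The cost is an amendment to two cells of the appendix with IRB approval (Section 12), and about two weeks of study meals per affected subject if recovery takes as long as Sections 1.3 and 5.3 describe. The 100% diet is already a study arm. Sample size and analysis do not change.

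If the sponsor has a reason for handling the two kinds of stop differently, stating it in Figure 6 would also resolve the point.
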